6.1.3 Preliminary Efficacy Assessment

6.1.3.1 Primary Hypothesis:

For efficacy, we hypothesize that the combination of panitumumab and talimogene laherparepvec will improve the response rate in advanced SCCS from 25% with single agent panitumumab [1] to 47% (near doubling of response rate to justify added expense and time required for administration of second drug as well as potential for additional toxicities).

Version Number: v10, March 23, 2023

Protocol Number: #091804

PI Name: [name]

Protocol Title: A Phase I Study of Talimogene Laherparepvec and Panitumumab in Patients with Locally Advanced Squamous Cell Carcinoma of the Skin (SCCS)

RESERVED FOR IRB STAMP

DO NOT MODIFY THIS SPACE

RUTGERS | eIRB
APPROVED

IRB Form Version 12.18.2018

Approval Date: 4/12/2023

Expiration Date: 9/21/2023

6.1.3.2 Sample Size Justification and Stopping Rules:

A detailed analysis for sample size justification is presented in Section 1.5.

The combination therapy approach would be considered to have limited safety if unanticipated toxicity from talimogene laherparepvec is observed. If the proportion of talimogene-laherparepvec related grade ≥ 3 toxicities that result in hospitalization or delays/cancellation of planned surgery is less than 30% of the subjects accrued, then the study accrual may continue. These toxicities do not include fever or injection site reaction which are known side effects of talimogene laherparepvec. The toxicity will be independently monitored by the Human Research Oversight Committee which will communicate any safety concerns directly to all participating Investigators.

6.1.3.3 Secondary endpoints to be captured include:

- To assess the clinical efficacy of panitumumab in combination with intratumoral talimogene laherparepvec in terms of immune-related progression-free survival (irPFS) at 12 months, overall response rate (ORR), 1-year survival, overall survival (OS) and time to resectability.
- To measure the pathologic complete response rate to panitumumab combined with talimogene laherparepvec.
- Assess the response of injected and non-injected tumor deposits after panitumumab and talimogene laherparepvec.
- Assess the time to initial response.
- Assess the durable response rate.
- To analyze the following molecular correlate with response to therapy to confirm mechanism of action, and identify potential future targeted strategies and biomarkers of response:
 - A) Mutation load in tumor tissue by next generation sequencing
 - B) DNA mutation signature in tumor tissue pre- and post-therapy by next generation sequencing
 - C) mRNA signature in tumor tissue pre-and post-therapy by Nanostring technology
 - D) Immune cell populations and immune profile in pre- and post-therapy tumor tissue and peripheral blood by flow cytometry and IHC

6.1.4 Outcome Measures:

All efficacy analysis will be based on the intention to treat population, which will include all enrolled patients. The primary outcome is the response rate to combination treatment with panitumumab and talimogene laherparepvec by RECIST 1.1 criteria in patients with advanced SCCS.

Secondary outcomes include best overall response rate, durable response rate and duration of response, progression free survival, overall survival in patients who receive panitumumab and talimogene laherparepvec. Molecular correlates will also be obtained and descriptive statistics applied.

PFS is defined as the number of months from the date of enrollment to the date of death or progression, whichever occurred earlier (per RECIST 1.1). If neither death nor progression is observed during the study, PFS data will be censored at the last valid tumor assessment. If patient is rendered disease free from surgical removal of tumor (section 1.3.2), progression is determined to be the date of diagnosis of recurrence.

Overall survival is defined as the time from the date of patient enrollment to date of death or the date last known alive.

Best Overall Response Rate (ORR) is defined as the best response as recorded from the start of study drug until disease progression. Patients without a post-baseline tumor assessment will be considered to be non-evaluable for best ORR. To classify best ORR as stable disease (SD), there should be a qualifying SD assessment at least 6 weeks from enrollment. Overall Response Rate (ORR) is defined as the proportion

Version Number: v10, March 23, 2023

Protocol Number: #091804

PI Name: [name]

Protocol Title: A Phase I Study of Talimogene

Laherparepvec and Panitumumab in Patients with
 Locally Advanced Squamous Cell Carcinoma of the
 Skin (SCCS)

47

RESERVED FOR IRB STAMP
 DO NOT MODIFY THIS SPACE

RUTGERS | eIRB
 APPROVED

IRB Form Version 12.18.2018

IRB ID: 102018002628

Approval Date:

4/12/2023

Expiration Date:

9/21/2023

of patients with a best ORR characterized as either a Complete Response (CR) or Partial Response (PR) relative to the total number of evaluable patients. Only patients with measurable disease at baseline will be included in the analysis of the objective response.

Durable response rate is defined as the percent of patients with complete response or partial response maintained continuously for a minimum of 6 months. Response duration is defined as the time from initial response until documented progression.

For subjects converted to resectable and surgical resection is performed (complete or partial), response endpoints will be censored at the time of surgery. However, these patients will still be followed for PFS and OS.

6.1.5 Toxicity Monitoring and Adverse Event Reporting:

All patients who receive one dose of protocol therapy will be evaluable for assessment of toxicity. Prior to each cycle, the treating physician will fully assess the patient's condition with respect to possible treatment related toxicities. All adverse events, whether observed by the physician or reported by the patient, occurring during the active portion of therapy, or up to 30 days after the last dose of treatment will be graded by a numerical score according to the NCI's Common Terminology Criteria for Adverse Events (CTCAE), Version 4.0 (see <http://ctep.cancer.gov/reporting/ctc.html>) and recorded in the patient's medical record. For the purposes of reporting laboratory abnormalities, only Grade 3-4 adverse events will be recorded on the adverse event CRF pages. Grade 1-2 laboratory abnormalities will not be recorded on the adverse event CRF pages. Information entered on the adverse event CRF pages will include:

- 6) Specific type and duration of reaction (i.e., start and stop dates, resolution)
- 7) Severity/grade
- 8) Relationship to study drug (causality, attribution)
- 9) Management of the event, if treated with medication and other actions taken to alleviate the clinical event
- 10) Whether or not it was considered a SAE

A preexisting condition is one that is present at the start of the study. A preexisting condition will be recorded as an adverse event if the frequency, intensity, or the character of the condition worsens during the study period.

6.1.5.1. Adverse Event Reporting Requirements:

An adverse experience is defined as any unintended or abnormal clinical observation that is not of benefit to the patient. Either the condition was not present prior to exposure to the study therapy, or it has worsened in intensity or frequency following exposure to the study therapy.

All "unexpected" (defined below) and/or "serious" (defined below) adverse events occurring during the active portion of therapy, or up to 30 days after the last dose of treatment, will be reported to the OHRS at [contact] or [contact]. Events will be promptly reported, in writing, to the local IRB in accordance with IRB policy. If a death or a life-threatening event occurs, the IRB will be notified within 24-hours of initial receipt of information. All other SAEs must be reported to the IRB within three to ten days of initial receipt of information. Written follow-up reports are required when additional information is needed to fully characterize the event. Copies of each report sent to the IRB will be kept in the study regulatory file.

In addition to reporting to the local IRB, reporting to external bodies such as industry and/or the FDA may be necessary. The Oncology group affiliates site will report all SAEs to the OHRS and will also be responsible for forwarding SAE reports to the IRB and FDA. In addition, information included in the SAE form will be provided to the PI/sponsor or its representative as soon as it is available. Moreover, an SAE line-listing will be sent to the PI/sponsor at least every 6 months.

Version Number: v10, March 23, 2023

Protocol Number: #091804

PI Name: [name]

Protocol Title: A Phase I Study of Talimogene

Laherparepvec and Panitumumab in Patients with
Locally Advanced Squamous Cell Carcinoma of the
Skin (SCCS)

48

RESERVED FOR IRB STAMP
DO NOT MODIFY THIS SPACE

RUTGERS | eIRB
APPROVED

IRB Form Version 12.18.2018

IRB ID:

Approval Date:

4/12/2023

Expiration Date:

9/21/2023

6.1.5.2 Reporting SAEs using commercially available drugs:

The PI shall notify the FDA of any adverse experience related to the use of Talimogene Laherparepvec and Panitumumab combination that is both serious and unexpected, as soon as possible and in no event later than 15 calendar days after the PI's discovery of the event. Each written notification may be submitted on FDA Form MedWatch 3500A <http://www.fda.gov/medwatch/safety/3500a.pdf> (fax # [name]). The PI shall also notify the FDA by telephone or by facsimile transmission of any unexpected fatal or life-threatening experiences associated with the use of Talimogene Laherparepvec and Panitumumab combination, as soon as possible but no later than 7 calendar days from the PI's discovery of the event information.

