4.0 Subject Considerations

4.1 Subject Selection and Enrollment Considerations

A. Recruitment Details

This protocol is open to both men and women, and all races.

B. Source of Subjects

Patients will be recruited from the Rutgers Cancer Institute of New Jersey, Robert Wood Johnson University Hospital, Duke University Medical Center - Duke Cancer Center, and NYU Langone Health.

C. Method to Identify Potential Subjects

A copy of the institution's IRB-approved informed consent document and written justification for any changes made to the informed consent for this protocol must be on file at the Rutgers Cancer Institute of New Jersey's Office of Human Research Services (OHRS) before any participating institution may enter patients.

To register eligible patients on this study, each site will contact OHRS. Contact information will be provided at the time of site activation. The signed and dated eligibility checklist, completed signature page of the consent form and additional source documents if requested by OHRS will need to be provided. Once OHRS verifies eligibility, the patient is considered on study. Patients must not start protocol treatment prior to enrollment.

If a patient does not receive any protocol therapy, baseline data will be collected and submitted on the pre-study and follow-up electronic case report forms (eCRF). The reason for not starting protocol therapy will be documented in the "follow-up eCRF." Case report form completion instructions and training will be provided to each participating institution prior to study activation at the participating institution.

D. Subject Screening

▪ Inclusion Criteria

A patient is eligible for enrollment if all of the following inclusion criteria are met:

- 1) Age 18 years or greater.
- 2) Histologically confirmed SCCS that is a) locally advanced or metastatic for which curative surgery or radiation would be difficult or impossible, or b) recurrent after initial surgery, chemotherapy, or radiation therapy, or c) considered to have aggressive features including the following: tumors 2 cm or more, tumors invading deep tissues such as muscle, cartilage or bone; tumors showing perineural invasion, and/or tumors metastatic to loco-regional lymph nodes. Patients may have had prior surgical interventions or been treated with investigational agents with residual or recurrent disease.

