- 3) Tumor suitable for direct or ultrasound-guided injection defined as at least one cutaneous, subcutaneous, or nodal lesion, or aggregate of lesions, ≥ 10 mm in diameter.

Version Number: v10, March 23, 2023

Protocol Number: #091804

PI Name: [name]

Protocol Title: A Phase I Study of Talimogene

Laheparpvec and Panitumumab in Patients with
Locally Advanced Squamous Cell Carcinoma of the
Skin (SCCS)

39

RESERVED FOR IRB STAMP
DO NOT MODIFY THIS SPACE

RUTGERS | eIRB
APPROVED

IRB Form Version 12.18.2018

Approval Date:

4/12/2023

Expiration Date:

9/21/2023

- 4) ECOG Performance Status \leq 2.
- 5) No prior treatment with panitumumab or talimogene laherparepvec for advanced disease.
- 6) Prior surgery or radiation is allowed if there is documented progression in the radiated/resected area or elsewhere by RECIST criteria v 1.1.
- 7) Measurable disease by RECIST criteria v 1.1.
- 8) Patients with a history of hematologic or solid organ transplant will be considered if they do not require high dose steroids or high dose immunosuppressants for disease control or control of transplant rejection, and have adequate hematologic, renal, and hepatic function as specified below. Current medications must be reviewed with transplant pharmacy team to exclude potentially serious interactions and case discussed with the study PI.
- 9) Patients with autoimmune disorders will be considered if they do not require high dose steroids or other immunosuppressants for disease control. Prednisone in daily doses up to 10 mg and inhaled steroids are acceptable.
- 10) Adequate organ function is required, as defined by ALL of the following:
 - a. -Absolute neutrophil count (ANC) \geq 1500/ μ L
 - b. -Platelet count \geq 100,000/ mm^3
 - c. -Hemoglobin \geq 9 g/dL
 - d. -Total bilirubin $<$ 1.5x institutional ULN; if patient has conditions of congenital hyperbilirubinemia, then patient must have isolated hyperbilirubinemia (e.g., no other liver function test abnormalities) with maximum bilirubin $<$ 2x institutional ULN
 - e. -AST or ALT \leq 2.5x institutional ULN in absence of liver metastases; \leq 5x ULN in presence of liver metastases
 - f. -Alkaline phosphatase $<$ 2.5x institutional ULN
 - g. -Creatinine $<$ 1.5x institutional ULN or calculated creatinine clearance \geq 60 mL/min as estimated using the Cockcroft-Gault formula.

▪ **Exclusion Criteria**

A patient is not eligible for enrollment if any of the following exclusion criteria are met:

- 1) Age $<$ 18 years.

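### Section 6.1.4 puts every efficacy analysis on all enrolled patients but divides ORR by evaluable patients only, which can raise the reported rate

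*Combined protocol and SAP*

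**What the plan says.** Section 6.1.4 (Outcome Measures) opens with a rule that has no exceptions: "All efficacy analysis will be based on the intention to treat population, which will include all enrolled patients". It names the RECIST 1.1 response rate as the primary outcome but gives no formula for it.

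The definitions that follow use other populations:

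- On evaluability: "Patients without a post-baseline tumor assessment will be considered to be non-evaluable for best ORR".
- On ORR, the proportion with a best response "characterized as either a Complete Response (CR) or Partial Response (PR) relative to the total number of evaluable patients".
- Directly after that: "Only patients with measurable disease at baseline will be included in the analysis of the objective response".

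Best response is "the best response as recorded from the start of study drug until disease progression".

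ORR is a secondary endpoint (sections 1.1 and 6.1.3.3). It is also the only plain CR-plus-PR rate that the plan defines operationally; the durable response rate additionally needs 6 months of maintained response.

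Section 4.1 fixes when a patient counts as enrolled: "Once OHRS verifies eligibility, the patient is considered on study". It also foresees patients who are never treated: "If a patient does not receive any protocol therapy, baseline data will be collected".

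The decision rule in section 1.5 is written in counts: stop if there are 3 or fewer responses in the first 13 patients, and declare success with 12 or more in 30.

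**The concern.** The all-enrolled denominator and the evaluable denominator differ as soon as one enrolled patient has no post-baseline tumor assessment, and nothing in the documents exempts ORR from the opening rule. An analyst would then have to break one of the two sentences.

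The error has one direction. Unassessed patients cannot be responders, so leaving them out removes only non-responders. In a single-arm study of 30, each exclusion visibly moves the percentage that readers will set against the 25% historical rate and the 47% target. A report could show a response count that fails the section 1.5 rule next to an ORR at or above the 40% that 12 of 30 represents.

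**Working it through.** **1. The plan's own design.** Inputs from section 1.5: p0 = 0.25, p1 = 0.47, n1 = 13, continue with 4 or more responses, N = 30, success with 12 or more. The exact success probability is the sum over x = 4 to 13 of P(Bin(13, p) = x) × P(Bin(17, p) ≥ 12 − x).

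- p = 0.25: 0.0468, within the stated 5%.
- p = 0.47: 0.8042, meeting the stated 80%.
- Chance of passing stage 1 at p = 0.25: 0.4157.

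The design reproduces. It uses counts among accrued patients, so the ORR wording does not alter it.

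**2. Who can drop out of the denominator.**

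- *Enrolled, never treated.* Section 4.1 counts the patient as on study once eligibility is verified. Best response runs only from the start of study drug, so this patient has none. This is the clearest case.
- *Left before first restaging.* Restaging comes after 9 weeks (sections 1.3.2 and 1.7.3.2). Whether these patients are evaluable depends on an undefined term: footnote 1 of Table 1 uses tumor assessment for scans, while the table also schedules a clinical tumor site assessment at treatment visits.
- *No measurable disease.* Few or none, because inclusion criterion 7 already requires "Measurable disease by RECIST criteria v 1.1".

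**3. Size of the shift.** With x responders and m non-evaluable non-responders among 30 enrolled, the all-enrolled rate is x/30 and the ORR as defined is x/(30 − m). The ratio is 30/(30 − m). The documents give no value for m, so it is varied here.

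| m (assumed) | ratio | ORR with x = 11 | ORR with x = 12 |
|---|---|---|---|
| 0 | 1.00 | 36.7% | 40.0% |
| 1 | 1.03 | 37.9% | 41.4% |
| 2 | 1.07 | 39.3% | 42.9% |
| 3 | 1.11 | 40.7% | 44.4% |
| 6 | 1.25 | 45.8% | 50.0% |

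Eleven responders fail the rule in every row. The smallest m that gives an ORR of at least 40% is 3 with 11 responders (11/27 = 40.7%), 5 with 10 (10/25 = 40.0%) and 8 with 9 (9/22 = 40.9%).

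**4. How often a failed count would sit beside an ORR of 40% or more.** Each patient is a responder, a non-evaluable non-responder (probability d) or an evaluable non-responder. The exact trinomial probability of at least 4 responders in the first 13, fewer than 12 in 30, and x/(30 − m) ≥ 0.40 is taken over all trials, not only those that pass stage 1. The documents give no d, and the answer depends on which rate is held at 25%.

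| d (assumed) | 25% among all enrolled | 25% among evaluable patients |
|---|---|---|
| 5% | 0.7% | 0.5% |
| 10% | 3.0% | 1.7% |
| 15% | 6.4% | 2.8% |
| 20% | 10.3% | 3.4% |

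In the first column the rate among evaluable patients is 0.25/(1 − d), which rises from 26.3% to 31.2% down the table. In the second, the all-enrolled rate is 0.25 × (1 − d).

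**The case against.** The strongest reply is that little depends on this. ORR is secondary, the go/no-go rule is in counts, alpha and power are as stated, and an evaluable-patient ORR is in common use. The size is assumed throughout: with one or two exclusions and 11 responders the ORR stays below 40%, and the plan sets no ORR threshold. The larger probabilities come from holding the all-enrolled rate at 25%; with 25% among evaluable patients they fall to 0.5–3.4%. Some patients who leave early may be evaluable through clinical or unscheduled assessments. Section 6.1.4 also describes the secondary outcomes as applying to patients who receive both drugs, which on one reading already leaves out the never-treated.

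Most of this stands as a limit on size, and it rules out any claim that type I error is inflated. It does not remove the contradiction. An evaluable-patient rate is acceptable under its own label, but here the plan promises all enrolled patients for all efficacy analysis and then defines something else. The phrase about patients who receive the drugs does not reconcile the two denominators; it is a third population wording that should be aligned in the same edit.

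**Conclusion.** The concern holds. Section 6.1.4 contains two incompatible denominators for ORR, and the evaluable one can only leave the reported rate unchanged or raise it. The increase is a factor of 30/(30 − m): about 3% in relative terms with one non-evaluable patient, 11% with three and 25% with six. If m = 0, nothing changes.

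The consequence is limited to the reported response percentage. The section 1.5 decision keeps its exact alpha of 4.7% and power of 80.4% if applied as written, to accrued patients. The conclusion about direction needs only that an unassessed patient is not a responder; the sizes rest on assumed numbers of non-evaluable patients. This should be corrected, but it does not invalidate the design.

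**What to change.** In section 6.1.4:

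1. Change the ORR denominator from evaluable patients to all enrolled patients, and count patients without a post-baseline tumor assessment as non-responders.
2. Delete the sentence limiting the analysis to measurable disease, or align it with the new denominator; the entry criterion already covers it.
3. State that the primary response rate uses the same all-enrolled denominator as the counts in section 1.5.
4. Align the wording that ties the secondary outcomes to patients who receive both drugs.
5. Keep the evaluable-only ORR as a labelled sensitivity analysis, reporting the number excluded and the reasons, and say whether a post-baseline tumor assessment means imaging only.

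The cost is a few sentences, with no new data and no change to the sample size or decision rule. The reported ORR may come out slightly lower than on the evaluable basis.

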1.0 Research Design

1.1 Purpose/Specific Aims

The purpose of this protocol is to serve as a phase I/II study of talimogene laherparepvec in combination with panitumumab in locally advanced or metastatic squamous cell carcinoma of the skin (SCCS). The primary hypothesis is that panitumumab, an antibody against Epidermal Growth Factor Receptor (EGFR), exhibits antitumor activity in patients with advanced squamous cell carcinoma of the skin and it may be enhanced when combined with talimogene laherparepvec, a HSV-1-derived oncolytic immunotherapy designed to selectively replicate within tumors and produce granulocyte macrophage colony-stimulating factor (GM-CSF) to enhance systemic antitumor immune responses, when delivered preoperatively. The overall treatment strategy described in this protocol is to treat locally advanced/unresectable SCCS with at least 3 cycles of talimogene laherparepvec in combination with panitumumab, and monitor patients for disease response. Patients will go on to surgical resection if adequate disease response is achieved; otherwise, patients who are receiving clinical benefit will be allowed to continue therapy. We will assess the safety, clinical efficacy and pathologic responses to treatment with talimogene laherparepvec in combination with panitumumab. The prospect is that the data derived from this study will lead to a large randomized trial testing the efficacy of this approach in this disease if this approach is tolerable with evidence of clinical efficacy, and that the correlates described in this protocol will identify potential candidate biomarkers of response to combination therapy.

A. Objectives

Primary:

- 1) To determine the safety of the combined treatment of talimogene laherparepvec and panitumumab.
- 2) To determine the preliminary efficacy of the combined treatment of talimogene laherparepvec and panitumumab, in comparison to single-agent panitumumab by historical control.

Secondary:

- 1) To assess the clinical efficacy of panitumumab in combination with intratumoral talimogene laherparepvec in terms of immune-related progression-free survival (irPFS) at 12 months, PFS hazard ratio, overall response rate (ORR), 1-year survival, overall survival (OS) and time to resectability.
- 2) To measure the pathologic complete response rate to panitumumab combined with talimogene laherparepvec.
- 3) Assess the response of injected and non-injected tumor deposits after panitumumab and talimogene laherparepvec.

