1.3 Research Design and Methods

We plan to enroll 30 patients with locally advanced SCCS. We will collect peripheral blood and biopsy tumor tissue from all patients prior to treatment. Patients will receive an initial dose of talimogene laherparepvec 10^6 PFU/mL on day 1 to seroconvert to HSV positive to reduce the rate and severity of injection reactions. On day 22, patients will begin combination therapy with panitumumab at 6 mg/kg and talimogene laherparepvec at 10^8 PFU/mL, followed by this schedule every 2 weeks for 3 cycles. Patients will then be evaluated for surgical resection after the administration of the third cycle of combinatorial therapy (approximately day 64). Surgery may commence at this time point, or the decision may be made by surgical and medical oncologist investigators to continue therapy for up to three more cycles if it is felt that the tumor may respond further with additional therapy. Patients who are not eligible for surgery are only allowed to continue protocol therapy past 3 cycles if clinical benefit, defined as partial response (PR), or stable disease (SD), is achieved. This also assumes that separate systemic options are not available for patient after protocol therapy of 3 cycles. We will collect tumor tissue again post-treatment, either at the

Version Number: v10, March 23, 2023

Protocol Number: #091804

PI Name: [name]

Protocol Title: A Phase I Study of Talimogene

Laherparepvec and Panitumumab in Patients with
Locally Advanced Squamous Cell Carcinoma of the
Skin (SCCS)

11

RESERVED FOR IRB STAMP
DO NOT MODIFY THIS SPACE

RUTGERS | eIRB
APPROVED

IRB Form Version 12.18.2018

IRB ID:

Approval Date:

[figure not shown]
4/12/2023

Expiration Date:

9/21/2023

time of surgical resection, if applicable, or by re-biopsy. Patients will also receive a biopsy at progression, if applicable (Figure 1). Peripheral blood will be collected prior to treatment, at the time of definitive surgery or biopsy, and at the time of progression, if applicable. Patients who are not resected but continue on protocol therapy will have PBMC sampled every three months or at progression if applicable.

Figure 1. Study Design

1.3.1 Study evaluation parameters and the schedules:

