1.7.3.2 Therapy with Panitumumab and Talimogene Laherparepvec

Patients who are eligible for and consent to enroll onto this trial will receive an initial dose of 10^6 PFU/mL of talimogene laherparepvec on day 1. On day 22 patients will begin combination therapy with panitumumab at 6 mg/kg and talimogene laherparepvec at 10^8 PFU/mL, followed by this schedule every 2 weeks +/- 3 days for 3 cycles. However, dosing windows for talimogene laherparepvec are Day 22 +/- 3 days for the initial dose and +/- 3 days for any subsequent cycles. Patients will receive therapy for a total of 9 weeks prior to first restaging scans and assessment for definitive therapy. The decision may be made to offer up to 3 more cycles of therapy prior to surgery if it is felt that the tumor may continue to respond.

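### Under 6.1.4 a converted patient resected on the planned schedule cannot count as a durable responder, 1.3.2 says otherwise, and the percentage has no rule for such patients

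*Combined protocol and SAP*

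**What the plan says.** Durable response rate is secondary objective 5 (section 1.1) and is listed again in 6.1.3.3 and 6.1.4. Section 6.1.4 gives the definition, "Durable response rate is defined as the percent of patients with complete response or partial response maintained continuously for a minimum of 6 months", and runs response duration from initial response to documented progression. It then adds: "For subjects converted to resectable and surgical resection is performed (complete or partial), response endpoints will be censored at the time of surgery". Those patients stay in follow-up for PFS and OS. Section 6.1.4 bases efficacy analyses on all enrolled patients, but divides ORR by evaluable patients.

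On who is operated on, section 1.1 says: "Patients will go on to surgical resection if adequate disease response is achieved". On timing, section 1.3 starts combination therapy on day 22, "followed by this schedule every 2 weeks for 3 cycles", and puts surgical evaluation at about day 64. Investigators may instead "continue therapy for up to three more cycles if it is felt that the tumor may respond further with additional therapy". Section 1.7.3.2 repeats that option. Section 1.3.2 puts the first response assessment after 9 weeks of treatment, which is the same point.

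Section 1.3.2 treats response after surgery differently. A patient made disease-free by surgery after 3 cycles is classed as a clinical complete response and followed for biopsy-proven recurrence. A patient who still has an index lesion after surgery continues response assessments.

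**The concern.** The patients sent to surgery are those who respond well enough, and under 6.1.4 surgery stops their response clock. If the clock starts at the visit where surgery is first considered, six months of response cannot build up before the operation. The reported durable rate would then depend partly on how many responders were resected, which is a different question from how long responses last. Response duration would be cut short in the same patients.

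The conflict with 1.3.2 adds a reproducibility problem. Two analysts could apply different sections to the same data and report different durable rates, each with textual support.

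**Working it through.** **Figures in the plan.** The plan gives no target for the durable rate, so there is no stated value to reproduce. Two related figures do reproduce:
- Evaluation day: 22 + 3 × 14 = day 64, as section 1.3 states.
- Primary design (section 1.5: 13 then 17 patients, stop at 3 or fewer responses, success at 12 or more of 30, 25% versus 47%): the exact two-stage binomial gives one-sided alpha 0.0468 and power 0.804, in line with the stated 5% and 80%. Durable response plays no part in it.

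**Observable response before planned surgery.**
- Required: 6 × 30.4375 = 182.6 days.
- Earliest response on the assessment schedule: about day 64 (window ±7 days, so days 57 to 71).
- Earliest durable date: 64 + 182.6 = about day 247 (days 240 to 254 across the window).
- Surgery after 3 cycles: about day 64, so about 0 days observed.
- Surgery after 6 cycles: 22 + 6 × 14 = day 106, so 106 − 64 = 42 days, or 6 weeks.
- Widest span, allowing 7 days at each end: 113 − 57 = 56 days, or 8 weeks (1.8 months).
- Generous limit, counting from day 1 before any response could exist: 113 − 1 = 112 days, or 3.7 months.

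Every span falls short of six months.

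**Effect on the rate.** Let R be the response rate, f the share of responders resected on the planned schedule, and q the share of unresected responders who hold for 6 months. The documents give neither f nor q, so both are assumptions. R = 47% is the plan's target. All resected responders are taken to fall under the censoring rule.
- All enrolled patients as denominator: R(1 − f)q
- Resected responders dropped: R(1 − f)q / (1 − Rf)

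| f | All enrolled, q = 100% | Dropped, q = 100% | All enrolled, q = 50% | Dropped, q = 50% |
|---|---|---|---|---|
| 0% | 47.0% | 47.0% | 23.5% | 23.5% |
| 25% | 35.2% | 39.9% | 17.6% | 20.0% |
| 50% | 23.5% | 30.7% | 11.8% | 15.4% |
| 75% | 11.8% | 18.1% | 5.9% | 9.1% |
| 100% | 0.0% | 0.0% | 0.0% | 0.0% |

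Example at f = 50%, q = 100%: 0.47 × 0.5 = 23.5%. With resected responders dropped, 0.235 / (1 − 0.235) = 30.7%.

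**Reading under 1.3.2.** If recurrence-free time after resection counted as maintained response, and resected patients held at the same q, the rate would be Rq for any f: 47.0% at q = 100% and 23.5% at q = 50%. At f = 50% and q = 100%, the same data could therefore give 23.5%, 30.7% or 47.0%.

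**The case against.** The strongest reply is that censoring at surgery is a defensible choice. It separates response to the drugs from removal of tumour by the surgeon, and conversion is credited elsewhere through time to resectability, pathologic complete response, PFS and OS. The endpoint is also secondary and descriptive. This stands as a reason not to merge post-operative disease-free time into the durable rate. It does not supply the missing rule for a binary percentage. A Kaplan-Meier estimate of duration would not fall mechanically, but censoring triggered by good response is informative, and the plan defines a percentage.

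A reader might also infer four stronger claims that the documents do not support:
- *No resected patient can ever be durable.* This follows from 6.1.4 only; 1.3.2 points the other way. Footnote 1 of Table 1 leaves surgical timing to the surgeon, so a late operation, at about day 247 or after, could follow a durable response. The censoring sentence covers patients converted to resectable, and inclusion criterion 2c admits patients on aggressive features alone, who are not clearly covered.
- *The plan counts resected responders as failures.* It says censored and does not specify the denominator for this endpoint.
- *The rate falls as the regimen succeeds.* That holds only if success means a larger resected share. At f = 50% and q = 100%, all enrolled, the rate rises from 12.5% at R = 25% to 23.5% at R = 47%.
- *The objective cannot be answered.* Eligibility includes patients for whom curative surgery is difficult or impossible. Section 1.7.3.3 lets non-candidates who benefit continue after 6 cycles, and unresected patients are imaged every 12 weeks, so they can reach six months.

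**Conclusion.** The point holds in a limited form. Under 6.1.4, a converted patient resected on the planned schedule has about 0 to 6 weeks of observable response, at most about 8, against the 26 weeks (182.6 / 7) required, and cannot be durable with either denominator. Section 1.3.2 contradicts the censoring, and the percentage lacks a rule for censored patients.

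The timing result needs only the protocol's own schedule. The size rests on the unknown resected share: the ceiling is little affected if few responders are resected and reaches zero if all are. No decision rule uses the endpoint, so the consequence is an ambiguous secondary result. It is worth correcting before analysis.

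**What to change.** Reconcile 6.1.4 with 1.3.2, and state in 6.1.4 how resected responders enter both the durable response rate and response duration, including the denominator and patients resected without having been converted. Then report:
- durable response in unresected responders, as the drug-only rate;
- on a separate line, the number of resected responders with pre-operative CR or PR, and how many are free of recurrence, progression and death at 6 months from first response. They are not counted as failures.

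Name the visit that settles the 6-month status. Follow-up imaging runs every 12 weeks from surgery, so after surgery at day 64 the visits fall near days 64 + 168 = 232 and 64 + 252 = 316, on either side of day 247. The first scheduled assessment on or after 6 months would serve.

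The cost is a few sentences and one table row. The data are already collected for PFS, and no treatment or surgical decision changes. The drawback is that the resected line includes the effect of surgery, so it must stay separate from the drug-only rate.
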